During the intervention period, participating PCPs will receive adolescent-centered communication training, based on the tenets of motivational interviewing, to reinforce healthy behavior choices and to engage youth and parents to reduce risk behaviors as appropriate. PCPs will also receive three feedback reports (baseline, 2 months and 4 months) on adolescent-reported receipt of counseling on each of the target behaviors and adolescent-reported visit satisfaction and follow-up care. PCPs will not be asked to complete any study questionnaires; all of the outcome data will be gathered directly from adolescents and caregivers. Outcome data for the three feedback reports will be given to providers in aggregate form and will be void of individual identifiers.

Adolescents in the intervention group will receive full personalized motivational feedback following completion of the screening survey, both with web-based delivery. Their PCPs will receive a summary report which will include specific information on the adolescent's responses that will allow them to reinforce healthy behavior choices and implement further brief, in-person interventions for moderate to high risk adolescents. The personalized feedback to the participant and provider is consistent with current standard of care. However, the electronic method of delivery is unique to this project.

In order to administer follow-up surveys, we will ask adolescents to provide an email address, cell phone number, or phone number. One day (T2) following their PCP appointment, adolescent participants will be asked via email, text message or phone to complete a survey about their motivation for health, perception of PCP communication, and experiences. Both adolescents and their caregivers will be asked about their satisfaction with treatment during the appointment with their PCP. In addition, caregivers will be asked open-ended questions to assess the provider's delivery of caregiver education regarding strategies to reduce health risks for their child during the visit.

Three (T3), six (T4) and twelve (T5) months following their PCP appointment, adolescent participants will be asked via email, text message or phone to complete all assessments

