3.2. Measures by Construct and Time point

Tables 1 and 2 describe the study measures by construct.

Table 1: Measures used in the study, organized by construct and method.

Measures and Constructs	Time point
Moderators	
Gender, age, race, household composition, school, truancy, support, goals, interest in discussing health risks with provider	T1(A)
Number of visits with provider	T2(A)
Health Self-Efficacy	T1(A), T2 (A), T3(A), T4(A), T5(A)
Caregiver Concerns	
Guidelines for Adolescent Preventative Services Caregiver Questionnaire: adolescent health risk behavior concerns.	T1(C)
Perception of provider engagement with the caregiver	T2 (C)
Intermediary Targets	
Health Motivation (Readiness to Change Rulers): Self-report used to assess adolescent motivation for change among specific health behaviors.	T1(A), T2 (A), T3(A), T4(A), T5(A)
Adolescent Report of the Visit: adolescent-report of the PCPs' delivery of risk behavior screening and counseling based on risk level.	T2 (A)
Interval Receipt of Care: adolescent self-report of extent of follow up care.	T3 (A), T4(A), T5(A)
Main Outcomes: Satisfaction & Perception of PCP Communication	

Satisfaction Questionnaire: self-report of satisfaction with care based on items adapted from the Consumer Assessment of Healthcare Providers and Systems (CAHPS) measure.	T2(A/C)
Adolescent Perception of Patient-Centeredness: adolescent self-report of how adolescents feel about visits with their primary caregiver.	T2(A)
Main Outcomes: Health Risk Dimensions*	
Alcohol Consumption and Marijuana Use: self-report based on items about typical quantity and frequency of drinking, smoking/using tobacco, and marijuana use (each calculated separately) over the past 30 days.	T1(A), T3(A), T4(A), T5(A)
Fruit and Vegetable Screener: self-report of fruit and vegetable consumption.	T1(A), T3(A), T4(A), T5(A)
Physical Activity Screener: self-report of physical activity.	T1(A), T3 (A), T4(A),T5(A)
Sexual Risk: self-report of sexual activity, birth control, and condom use.	T1(A), T3(A), T4(A), T5(A)
Patient Health Questionnaire-9 (PHQ-9): self-report of DSM-V symptoms for depression.	T1(A), T3(A), T4(A), T5(A)
Safety: self-report to assess behaviors that contribute to unintentional injuries (e.g., seat belt use, helmet use).	T1(A), T3(A), T4(A), T5(A)

Key: T1 = Timepoint 1 (Baseline) T4 = Timepoint 4 (6 month)
T2 = Timepoint 2 (1-day) T5 = Timepoint 5 (1 year)
T3 = Timepoint 3 (3-month)
A = Adolescent survey

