intervention effects. Data set documentation will then be developed and distributed to the study team. Before carrying out analyses addressing each of the research questions, an analysis plan will be formally presented to the study team and Project Advisory Board so a wide range of expertise and experience is brought to bear on each work product of the team.

Some key features of the stepped wedge design require special consideration in the planned analyses. First, the design involves unidirectional cross-over from the control arm to the intervention arm for all PCPs. This has to be captured by an indicator specific to PCP and time point. Second, there are natural hierarchical structures in the data with PCPs nested within clinics, patients nested within PCPs, and repeated assessments made within patients for some outcomes, such as health risk behaviors. Because different patient samples will be surveyed at each time point, within patient correlation over time should not be strong. Still, clustering at the clinic and PCP-levels needs to be examined in all analyses. Third, secular time trends need to be carefully examined and separated from the intervention effect. Based on these considerations, we will focus on model-based approaches (linear or generalized linear mixed effects models) for the main analyses, in addition to standard hypothesis testing techniques.

Aim 1 will compare intermediary targets at all clinics before and after the intervention using an analytic approach that both accounts for design features, repeated assessments within adolescents, time trends in these target behaviors during study period and adjust for potential confounders. For this aim we will use patients as the units of analysis. We will consider outcomes at the level of the patient (adolescent reported motivation for health and provision of appropriate preventive counseling).

Our primary analysis will be based on a set of mixed effects regression models. As an illustration, let's consider the adolescent self-reported health motivation (readiness to change, as other adolescent reported outcomes can be modelled in a similar fashion. Specifically, we will consider the following regression model:

$$Y_{ijk} = \mu + \alpha X_{ijk} + \beta_k T_k + \gamma_k X_{ijk} * T_k + b_i + b_{ij} + \varphi \text{Covariates} + \varepsilon_{ijk},$$

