in which Y_{ijk} denotes the health motivation reported by j th patient within i th provider at k th time interval, X_{ijk} is a binary indicator of exposure to the intervention for the provider and the predictor of interest, T_k is a binary indicator of the k th assessment, b_i and b_{ij} are PCP and adolescent specific random effects that account for the within PCP and within adolescent correlations, and ε_{ijk} is the error term. Additional patient-level or PCP-level confounding variables can be adjusted in the model as well.

With this model, the fixed effects α captures the treatment effects on mean responses and time-by-intervention interaction coefficients γ_k 's captures the treatment effects across time. Fixed effects β_k 's aim to capture any temporal trend or learning effects. Using this approach, both within-adolescents and between adolescents information will be used to estimate the treatment effects. All coefficients will be tested using Wald test. Also note this

model framework is flexible enough that a patient can be enrolled at any time during the study and the model can accommodate different numbers of post-intervention assessments. For example, for an adolescent enrolled after his/her PCP has received intervention, all X_{ijk} 's would take value 1 for that subject.

We will apply linear mixed effects models for Gaussian outcome Y_{ijk} , and generalized linear mixed effects models for other types of outcomes (e.g., logistic model for binary outcome).

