Web-based surveys will be accessed by logging on to a secure server with security and data integrity violations obviated by requiring participants to log in with a password unrelated to any identifying information on any on-line page or database. All information transferred between client and server machines will be secured using 128-bit encrypted Secure Sockets Layer. All data stored in the online repository will be encrypted using the official Advanced Encryption Standard algorithm. Protocols have been informed by prior internet-based studies conducted by study investigators.

For participants enrolled in the post-implementation period, their baseline report will be printed by study or participating clinic staff and given to the participant's PCP prior to their appointment. Participant reports will be shared with PSPRN staff via a protected, designated fax machine available only to clinic staff and providers or through a secure server with security and data integrity violations obviated by requiring them to log in with a password unrelated to any identifying information related to the research participant. All information transferred between client and server machines will be secured using 128-bit encrypted Secure Sockets Layer. All data stored in the online repository will be encrypted using the official Advanced Encryption

Standard algorithm. Protocols have been informed by prior internet-based studies conducted by study investigators.

For purposes of analysis and manuscript preparation, paper data files will be maintained for up to 3 years after the project ends, after which all paper data will be disposed of via shredding. Secure electronic data files will be kept for up to 7 years after the project ends on SCRI's secure network.

5. Risk/Benefit Assessment

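### For outcomes measured at T1, α is read as the treatment effect although X = 1 before the visit, and no coding, reference assessment or deciding contrast is stated

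*Combined protocol and SAP*

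**What the plan says.** Section 3.3.2 gives the Aim 1 model with an intercept, exposure X, assessment indicators T_k, the X×T_k products, random effects for PCP and adolescent, and covariates. It says that "α captures the treatment effects on mean responses and time-by-intervention interaction coefficients γ_k 's captures the treatment effects across time". On the coding of exposure it says that "for an adolescent enrolled after his/her PCP has received intervention, all X_{ijk} 's would take value 1 for that subject". On testing it says only: "All coefficients will be tested using Wald test".

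Table 1 in section 3.2 lists health motivation ("Self-report used to assess adolescent motivation for change among specific health behaviors") at T1 to T5, and the health risk measures at T1, T3, T4 and T5. Section 3.3.2 extends the Aim 1 framework to the individual risk behaviours and counts baseline among the outcome times.

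T1 comes before exposure. Section 3.1 says: "Adolescents in the intervention group will receive full personalized motivational feedback following completion of the screening survey". Section 4.4 says of post-implementation participants that "their baseline report will be printed by study or participating clinic staff and given to the participant's PCP prior to their appointment".

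Section 3.3.3 gives a form without the interaction, reads its α as the treatment effect, and says that similar models will serve for adolescent outcomes. Its worked example is a PCP counselling rate.

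**The concern.** Once X×T_k is in a model, the coefficient of X alone has no fixed meaning until the coding of T_k is chosen. The plan gives α a meaning without choosing. With T1 as reference, α compares adolescents enrolled in different periods before any of them has had the feedback or the visit.

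The stated reading could then present a pre-visit difference as the treatment effect, or report a real effect as null or diluted. A reader cannot tell which coefficient or contrast settles Aim 1 motivation or the Aim 2 individual risk behaviours. If the choice is left until the data are seen, it also allows selection among several Wald tests.

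**Working it through.** The plan gives no figure to reproduce here, since it states no effect size, SD, ICC or power. The question is what each coefficient estimates.

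**Inputs from the documents.** Motivation has five assessments (T1 to T5, Table 1). Each risk behaviour has four (T1, T3, T4, T5). T1 precedes feedback and visit (sections 3.1 and 4.4). X = 1 on every row for adolescents enrolled after their PCP's intervention (section 3.3.2).

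**Assumptions.** Linear model, X fixed at the index visit, complete data, and a true effect of 0 at T1 and δ at each later assessment. The within-adolescent correlation r is exchangeable and not given in the documents, so r = 0.1 to 0.7 is shown.

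**Step 1: a constraint is needed.** As written for motivation, the fixed part has 1 + 1 + 5 + 5 = 12 columns. Two exposure groups at five assessments give 10 cell means, so the rank is 10. Two constraints are required and none is stated.

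**Step 2: α under each coding.** Let D_k be the exposed-minus-unexposed difference at assessment k, so D_T1 = 0 and D_k = δ afterwards. Under reference coding, α = D_ref and γ_k = D_k − D_ref. Under sum-to-zero coding, α is the mean of the D_k.

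| Coding | α, four assessments | α, five assessments |
|---|---|---|
| T1 as reference | 0 (each γ_k = δ) | 0 (each γ_k = δ) |
| Sum-to-zero | (0 + 3δ)/4 = 0.75δ | (0 + 4δ)/5 = 0.80δ |
| A post-visit reference | 1.00δ, that assessment only | 1.00δ, that assessment only |

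**Step 3: no effect, but a persistent difference d between enrolment periods.** Here D_k = d at every assessment. Then α = d under each coding above, while the average γ_k with T1 as reference is d − d = 0.

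**Step 4: the form without interaction, if it is used with T1 rows kept.** With complete data α is the average of the D_k, again 0.75δ or 0.80δ. The X×Group coefficient shrinks likewise: a true subgroup difference of 0.40 becomes 0.40 × 0.75 = 0.30 or 0.40 × 0.80 = 0.32.

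**Step 5: precision of the remedies** (variances up to a common factor, no clustering, T3 to T5 averaged).

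- Mean γ: (1 + 2r)/3 + 1 − 2r = 4(1 − r)/3.
- T1 as covariate: (1 + 2r)/3 − r² = (1 − r)(1 + 3r)/3.
- Information of mean γ relative to the covariate analysis: (1 + 3r)/4, which is 0.325, 0.475, 0.625 and 0.775 at r = 0.1, 0.3, 0.5 and 0.7.
- Diluted four-assessment α: signal² over variance is 0.75²/((1 + 3r)/4) = 2.25/(1 + 3r), against 0.75/(1 − r) for mean γ. They are equal when 2.25(1 − r) = 0.75(1 + 3r), so r = 1/3. Below that, mean γ has less power than the diluted α.

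**Step 6: with fixed clinic and period terms** (six assumed equal one-clinic steps, equal enrolment, ICC 0; the rollout figure is not shown). Period terms leave 0.556 of the variance of X; clinic and period terms together leave 0.317. A clinic effect shared by T1 and follow-up cancels from mean γ, so its variance rises by 1/0.556 = 1.8. For T1 as covariate the rise is 1/0.317 = 3.15 at every r. The relative information of mean γ becomes (1 + 3r)/4 × 3.15/1.8, which is 57%, 83%, 109% and 136% at the same values of r. It passes 100% at r = (4/1.75 − 1)/3, about 0.43.

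**The case against.** The γ_k are estimated, Wald-tested and described as treatment effects across time. With T1 as reference the whole effect therefore sits in coefficients that the plan already reports. The phrase about mean responses fits sum-to-zero coding at least as well as reference coding, and there α is diluted but not zero. X is defined as the provider's exposure, so X = 1 at T1 follows the plan's definition. The model is introduced as an illustration, and section 3.3.2 promises a formally presented analysis plan before each research question is analysed.

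Much of this stands. A reader might infer that the planned analysis must return a null result, or that the plan overlooks the γ_k. The text supports neither: a zero α needs T1 as reference, and a null report also needs the γ_k to be set aside. What does not fall away is that α is the coefficient assigned the effect on mean responses, that nothing says which contrast decides, and that sum-to-zero coding still averages in a row where the effect cannot yet exist. Section 3.3.2 bases the primary analysis on models of this kind. The later plan is not in these documents and would have to reverse a reading already given.

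**Conclusion.** The point holds as a gap in specification joined to a reading of α that is wrong under some admissible codings. It should be fixed. With a constant post-visit effect δ and X fixed at the index visit, the same stated coefficient runs from 0 to 1.00δ depending on an unstated choice, with 0.75δ or 0.80δ between. This does not depend on r. Step 3 adds that a persistent difference between enrolment periods enters α in full.

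The part on section 3.3.3 is conditional. A reader might infer that its treatment-effect and subgroup estimates are diluted in general, but its worked example has no T1 row. The factors 0.75 and 0.80 apply only if that form is used for T1-row outcomes with the T1 rows kept and data complete. A reader might also infer that α could change sign if X followed the PCP's status over time. That would need several further conditions that the plan does not state, so it is not claimed.

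Confidence is high that the coding and contrast are missing. It is lower for the consequences, which depend on choices not yet made.

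**What to change.** For health motivation and the individual risk behaviours:

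- Code X by exposure at the index visit.
- Replace α as the stated treatment effect with one named post-baseline contrast. Either declare T1 the reference and use the average of the post-visit γ_k (for example T3 to T5, each also reported), or analyse the post-baseline rows with T1 as a covariate.
- In section 3.3.3, use the matching contrast for X×Group wherever the outcome has a T1 row.

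This is a change of wording and needs no new data. The cost is in precision and differs between the options. Without clinic and period terms, mean γ carries 33% to 78% of the information of the covariate analysis over r = 0.1 to 0.7. With fixed clinic and period terms, under the assumptions of step 6, the covariate analysis is the more precise only below r of about 0.43.

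The remark that "Because different patient samples will be surveyed at each time point, within patient correlation over time should not be strong" should not settle the choice, because it refers to different samples and not to repeated assessments of one adolescent. Section 3.3.2 also asks that "secular time trends need to be carefully examined and separated from the intervention effect". Change from baseline removes only persistent differences, so whether to carry clinic and period terms should be decided together with the contrast, before analysis.

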3.1. Study Design

This study will evaluate the effect of I-ACT with Check Yourself on adolescent-perceived quality of care (i.e., satisfaction and perception of PCP communication), motivation for health, and health risk behaviors using a stepped wedge study design. The study will take place in 6 participating PSPRN affiliated clinics, where the system of interventions (I-ACT with Check Yourself) will be rolled-out sequentially to the clinics, chosen in random order, over spaced time intervals (see Figure 1). We refer to pre-implementation of I-ACT with Check Yourself, as the control period and post-implementation as the intervention (i.e., case) period.

Figure 1: Stepped Wedge Study Design and Timeline

We anticipate that approximately 30% of youth approached will participate in the study. Thus, we will invite approximately 1000 adolescent/caregiver dyads to participate in the study, in order to yield 300 adolescent/caregiver dyad participants in our total sample. Upon enrollment, caregiver participants will be asked to complete a brief (10-minute) web-based questionnaire about their education/occupation, their adolescent's health history, and an open-ended question about what they would like to get from PCPs for themselves and their adolescent. Adolescents who enroll in the study will receive either electronic health screening alone (i.e., control group) if

their clinic appointment occurs in the pre-I-ACT implementation period or Check Yourself (i.e., intervention group) if their clinic appointment occurs in the post-implementation period.

At baseline (T1), adolescents will be asked to complete a web-based screening survey that includes questions about guideline-recommended health risk behavior screening areas, including substance use, nutrition, physical activity, sexual behavior, depressive symptoms, and safety. The screener questions themselves are current standard of care. Adolescents will also be asked to report their age, gender, race/ethnicity, interest in discussing health risks with the PCP, and self-efficacy.

Adolescents in the control group will complete the web-based screening survey for research purposes, but neither they nor their PCP will receive feedback about their health behaviors. PCPs will screen and counsel the patient as they would normally do under usual care conditions, consistent with the current standard of care.

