For *Aim 2*, analyses will be based on patient survey responses to the 8-item satisfaction scale, patient perception of PCP communication, and the summary health risk variable, which will all be treated as continuous response variables. The summary health risk variable constructed from a count of dichotomized key risk behaviors (as shown in Table 2). First, satisfaction levels and risk behaviors will be summarized for each period (pre- and post-intervention) and will be compared using two sample t-tests. For the main analysis, we will apply mixed effects models similar to those proposed in Aim 1 to examine the intervention effect. For patient satisfaction, PCP satisfaction, adolescent's perception of PCP communication and health risk behaviors, the analysis will be cross-sectional comparisons at one day following the primary care visit. Let Y_{ij} denotes the satisfaction at one-day post visit of adolescent j within PCP i , let X_{ij} denote whether the PCP has received intervention at the time of visit, then the following mixed effects model can be applied

$$Y_{ij} = \mu + \alpha X_{ij} + b_i + \varphi \text{Covariates} + \varepsilon_{ij},$$

where b_i accounts for within-PCP correlations for adolescents seen by the same PCP. The fixed effect α captures the intervention effect on the patient satisfaction. Similar model can be applied to PCP outcomes and we can account for within-clinic correlations as well.

When examining the intervention effects on adolescents individual risky behaviors (alcohol use, marijuana use, unprotected sexual activity, depression, physical activity, healthy food consumption, seatbelt and helmet use) at baseline, 3, 6, and 12 months after the primary care visit, same modeling framework as outlined for Aim 1 can be applied.

3.3.3 Heterogeneity of Treatment Effects.

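### The preliminary pre/post t-tests in Aim 2 ignore clustering and pick up part of any secular trend, and the one-day mixed model as written does not remove that trend either

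*Combined protocol and SAP*

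**What the plan says.** Section 3.1: "The study will take place in 6 participating PSPRN affiliated clinics", and the intervention is "rolled-out sequentially to the clinics, chosen in random order, over spaced time intervals". Figure 1, which gives the step layout, is not visible in the text available.

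Section 3.3.2, general part, sets two requirements for this design: "clustering at the clinic and PCP-levels needs to be examined in all analyses", and "secular time trends need to be carefully examined and separated from the intervention effect". It gives model-based methods the lead role "for the main analyses, in addition to standard hypothesis testing techniques".

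Section 3.3.2, Aim 2: satisfaction and risk behaviours are summarised for each period and "will be compared using two sample t-tests". The next sentence reads: "For the main analysis, we will apply mixed effects models similar to those proposed in Aim 1 to examine the intervention effect". The model then written out for one-day outcomes has an intercept, an intervention indicator, a PCP random effect, covariates and an error term. It has no time term, and within-clinic correlation is described only as something that can be accounted for.

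**The concern.** In a sequential roll-out, post-implementation visits are later on average than pre-implementation visits and come disproportionately from the clinics that crossed early. A pooled two-sample t-test therefore mixes the intervention effect with calendar drift and with differences between clinics, and its standard error treats adolescents who share a PCP or clinic as independent. The plan asks for both features to be dealt with, then schedules a test that deals with neither.

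The resulting p-value would be reported beside the mixed-model result, with no rule for disagreement. Agreement would not reassure either: if the main model also lacks a time term, both analyses carry much the same trend bias, and one may appear to confirm the other.

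**Working it through.** **Inputs from the protocol.** 6 clinics, about 30 PCPs (about 5 per clinic) and about 300 adolescents (sections 2.1 and 3.1), hence 50 per clinic and 10 per PCP. The plan states no ICC, trend, SD or alpha for this comparison, so there is no figure of its own to reproduce.

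**Assumptions.** Total SD 1; two-sided 5%; no true effect; even enrolment; one clinic crossing at a time over seven equal periods (alternative: three steps of two clinics over four periods); linear drift.

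**Share of drift absorbed, six steps.** Clinic c (1 to 6) has c pre periods and 7 − c post periods, giving 21 pre and 21 post clinic-periods, or 150 adolescents each.
- Mean pre period: (1+3+6+10+15+21)/21 = 56/21 = 2.667.
- Mean post period: (6×28 − 56)/21 = 112/21 = 5.333.
- Difference 2.667 periods: 2.667/6 = 44% of the drift from first to last period, or 2.667/7 = 38% of the drift over the whole duration.

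**Three steps.** Means 20/12 = 1.667 and 40/12 = 3.333; difference 1.667. Shares: 1.667/3 = 56%, or 1.667/4 = 42%.

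**Clustering, six steps.** Clinic c's weight in the post mean minus its weight in the pre mean is (7 − 2c)/21, that is 5, 3, 1, −1, −3, −5 over 21. The sum of squares is 70/441 = 0.159. Hence

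Var(difference) = 0.159·ICC(clinic) + (0.159/5)·ICC(PCP) + (1 − ICC(clinic) − ICC(PCP))·(2/150).

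The t-test instead uses about √(2/150) = 0.115 as its standard error. At 0.05/0.05 the true variance is 0.0079 + 0.0016 + 0.0120 = 0.0215, so the SD is 0.147. The critical difference, 1.96 × 0.115 = 0.225, is then only 1.53 true SDs, and rejection is about 12.5%.

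A 0.3 SD first-to-last drift adds a bias of 0.444 × 0.3 = 0.133 SD. (This equals 0.3 × 7/6 = 0.35 SD over the whole duration.)

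| Clinic/PCP ICC | True SD of difference | Rejection, no trend: formula | Rejection, no trend: simulation | Rejection, 0.3 SD drift: formula |
|---|---|---|---|---|
| 0/0 | 0.115 | 5% | about 5% | 21% |
| 0.02/0.03 | 0.130 | 8% | about 8% | 24% |
| 0.05/0.05 | 0.147 | 12.5% | about 14% | 27% |
| 0.10/0.05 | 0.170 | 19% | about 19% | 31% |

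Simulations used 4,000 trials per setting. Repeat runs gave 8-9%, 12-14% and 18-21% for the three non-zero ICC pairs without trend, and about 21-32% across the table with the 0.3 SD drift. With three steps the no-trend simulated figures are 7-8%, 10-11% and 16-17%.

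**One-day model.** Simulated for six steps at clinic/PCP ICCs of 0.02/0.05 and 0.05/0.05, with known variance components and 1,500 trials per setting. Trends here are over the whole duration.

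| Model | Rejection, no trend | Rejection, 0.2 SD | Rejection, 0.4 SD | Bias at 0.2 / 0.4 SD | SE |
|---|---|---|---|---|---|
| As written (PCP effect, no time) | about 7% | 11-13% | 30-31% | 0.08-0.09 / 0.17 SD | 0.12-0.13 |
| With period, clinic and PCP terms | about 6% | 4-5% | about 6% | about 0 / about 0 | 0.18-0.19 |

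The PCP effect repairs most of the clustering problem. The trend bias remains until calendar period enters the model.

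**The case against.** The strongest reply is that the t-test is only a preliminary step. Section 3.3.2 names mixed models as the main Aim 2 analysis in the very next sentence and ties no conclusion to the t-test. That stands. A reader might infer that Aim 2 rests on t-tests and that its results are therefore invalid; the text does not support this.

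Three other strong readings also fail.
- The t-test does not absorb the whole trend, only the share shown above.
- The inflation is conditional. With no ICC and no trend the test holds its level, and the plan quantifies neither. Its own text, however, treats both as needing attention.
- Repeated measures do not affect every outcome. Table 1 collects satisfaction and perceived patient-centredness at T2 only, so the issue can arise only for risk behaviours (T1, T3, T4, T5). The t-test sentence names no time point, but nothing says that assessments are pooled.

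It can also be argued that the main model makes the t-test harmless, because it is to resemble the Aim 1 model and covariates could include time. But the one-day equation shows no time term, and the Aim 1 time indicator is defined by assessment, not clearly by calendar period. The defence relies on a term that has not been written down.

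**Conclusion.** The point holds as a correctable flaw in a stated secondary test, together with a gap in the main one-day model. The t-test p-values cannot be relied on. Under the six-step layout, false rejection runs from about 8% to 19% through clustering alone and about 21-32% with a 0.3 SD first-to-last drift. These sizes rest on assumed ICCs, drift, step layout, even enrolment and alpha; only the direction follows from the design.

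The t-tests do not by themselves overturn the main Aim 2 inference. Nor would removing them settle the matter, since the written one-day model leaves the trend bias in the satisfaction and communication results. The model simulations treated variance components as known, so a model fitted with six clinics may perform somewhat worse than shown.

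**What to change.** 1. Keep the pre/post summaries as description, tabulated by clinic and calendar period, and delete the two-sample t-tests.
2. Write calendar-period fixed effects and a clinic random effect into the one-day Aim 2 model, alongside the PCP effect. Given six clinics, name a small-sample correction for the test of the intervention effect.
3. State that all Aim 2 hypothesis tests come from the mixed models.

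Deleting the t-tests costs nothing. Calendar period can be coded from the visit date, which is already needed to set the intervention indicator. The real cost is precision: the standard error rises from about 0.12-0.13 to 0.18-0.19 SD (for example 0.184/0.127 = 1.45 times). That is the honest precision of this design once time is separated from the intervention.
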